- Presence of signs or symptoms that could confound or confuse assessment of study vaccine reactogenicity. For subjects with injection site or systemic signs or symptoms, or with an acute illness, including an oral temperature greater than or equal to 100°F, the second study vaccination should be postponed/deferred until signs, symptoms or acute illness have/has resolved, or are/is improving as further specified below, and if within the acceptable protocol-specified window for the Dose 2 visit. No exceptions to the protocol-specified window will be made. **Note for afebrile, acute illness only:** If a subject is afebrile, his/her acute illness is nearly resolved with only minor residual symptoms remaining, this occurs within the acceptable protocol-specified window for the Dose 2 visit, and, in the opinion of the site PI or appropriate sub-investigator, the residual symptoms will not interfere with the ability to assess safety parameters as required by the protocol, the subject may receive the second study vaccination without further approval from the DMID Medical Officer. No exceptions to the protocol-specified window will be made.

- Grade 3 solicited or unsolicited AE that occurs without alternative etiology in the 8 days after the first study vaccination.
- Grade 3 solicited or unsolicited AE that is ongoing, whether or not it is improved or resolving.
- Any unresolved or ongoing Grade 2 solicited or unsolicited AE that does not decrease to Grade 1 or less prior to the second study vaccination. Note: An unresolved or ongoing Grade 1 solicited or unsolicited AE is permissible following the documented determination by the site PI or appropriate sub-investigator, that it would not render study vaccination unsafe or interfere with the evaluation of responses.
- Grade 3 clinical safety laboratory value (according to the toxicity table, [Section 9.2.3](#)) that does not decrease to Grade 2 or less prior to the second study vaccination. Note: Any clinical safety laboratory parameter may be re-evaluated only once at the central (clinical) laboratory in order to assess eligibility prior to the second study vaccination. If the clinical safety laboratory value decreases to Grade 2 or less, the subject may receive the second study vaccination. The second study vaccination should be scheduled to occur within the acceptable protocol-specified window for the Dose 2 visit. No exceptions to the protocol-specified window will be made.

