Height and weight will be collected at the screening visit (optional) or on Day 1 prior to the first study vaccination for the calculation of BMI.

Reactogenicity assessments will include an assessment of solicited AEs occurring from the time of each study vaccination through 7 days after each study vaccination, which includes an

assessment of injection site reactions including pruritus (itching), ecchymosis (bruising), erythema (redness), induration (hardness), edema (swelling), pain, and tenderness as well as systemic reactions including fever, feverishness (chills/shivering/sweating), fatigue (tiredness), malaise (general unwell feeling), myalgia (body aches/muscular pain exclusive of the injection site), arthralgia (joint pain exclusive of the injection site), headache, and nausea. Pre-administration reactogenicity assessments will be performed immediately prior to each study vaccination to establish baseline, then the study vaccination will be given.

Subjects will be observed in the clinic for at least 20 minutes after each study vaccination. The study vaccination site will be examined, post-administration reactogenicity assessments will be performed, and any AE/SAEs will be recorded on the appropriate DCF prior to discharge from the clinic. The study vaccination site will also be examined approximately 1, 3 and 7 days after each study vaccination.

All subjects will complete a Memory Aid from the time of each study vaccination through 7 days after each study vaccination. Memory Aids will be reviewed with the subjects for any AEs (solicited injection site and systemic reactions as well as unsolicited AEs), SAEs and concomitant medications (including solicitation for receipt of any non-study influenza vaccines) approximately 1, 3 and 7 days after each study vaccination via phone call or clinic visit.

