9.2 Methods and Timing for Assessing, Recording and Analyzing Safety Parameters

9.2.1 Adverse Events

Adverse Event (AE): ICH E6 GCP defines an AE as any untoward medical occurrence in a patient or clinical investigation subject administered a pharmaceutical product regardless of its causal relationship to the study treatment. The FDA defines an AE as any untoward medical occurrence associated with the use of a drug in humans, whether or not considered drug related.

An AE can therefore be any unfavorable and unintended sign (including an abnormal laboratory finding), symptom or disease temporally associated with the use of a medicinal (investigational)

product. The occurrence of an AE may come to the attention of study personnel during study visits and interviews of a study recipient presenting for medical care, or upon review by a study monitor.

AEs, including solicited injection site and systemic (subjective and quantitative) reactions, not meeting the protocol-defined criteria for SAEs, will be recorded on the appropriate DCF and entered into the eCRF. Information to be collected for unsolicited non-serious AEs includes event description, date of onset, licensed study physician's assessment of severity and relationship to study product or alternate etiology (if not related to study product) (assessed only by those with the training and authority to make a diagnosis and listed on the Form FDA 1572 as the site PI or sub-investigator), date of resolution, seriousness, and outcome. AEs occurring during the trial-collection and reporting period will be documented appropriately regardless of relationship to study product. AEs will be followed through resolution.

Any medical condition that is present at the time that the subject is screened will be considered as baseline and not reported as an AE. However, if the severity of any pre-existing medical condition increases, it will be recorded as an AE.

AEs must be assessed for severity and relationship to study product (see definitions below). AEs characterized as intermittent require documentation of onset and duration of each episode. The start and stop date of each reported AE will be recorded on the appropriate DCF and entered into the eCRF.

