11.6.2 Safety Data

Summaries and analysis of safety data will be presented for the Safety Analysis Population. All summaries and analyses will be presented for all subjects.

Solicited AEs will be summarized by severity for each day after each study vaccination (Days 1-8 post each study vaccination) and as the maximum severity over all 8 days. Additionally, solicited AEs will be analyzed by taking the most severe response over the follow-up period, dichotomizing into a binary variable (none versus mild, moderate or severe) and using standard techniques, such as exact CIs, to summarize the proportion of subjects reporting each symptom, any injection site symptom and any systemic symptom. Summaries of solicited AEs will be presented separately for each study vaccination as well as overall study vaccinations by

treatment arm. The proportion of subjects reporting symptoms may be compared between treatment arms using Chi-square or Fisher's exact test. The proportion of subjects reporting solicited symptoms between the different study vaccinations (i.e., first and second) will be compared using McNemar's test.

Unsolicited AEs will be coded by Medical Dictionary for Regulatory Activities (MedDRA[®]) for preferred term and system organ class (SOC). The numbers of SAEs and MAAEs, including NOCMCs and PIMMCs, are likely to be small in this trial and will be reported by detailed listings showing the event description, MedDRA[®] preferred term and SOC, relevant dates (study vaccinations and AEs), severity, relatedness, and outcome for each event. Non-serious unsolicited AEs will be summarized as number and percentage of subjects reporting at least one event in each MedDRA[®] preferred term and SOC, cross-tabulated by severity and relationship to study product. Additionally, the proportion of subjects and exact 95% CIs of AEs in aggregate and by MedDRA[®] categories will be computed.

Clinical laboratory data will be summarized by severity for each visit and as the maximum over all post-study vaccination visits. Graphical presentations may include box plots.

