9.3.1. Solicited Events and Symptoms

Systemic solicited adverse events were collected pre-vaccination, and systemic and local solicited adverse events were collected at-least 20 minutes post-vaccination and then daily for 7 days after each vaccination and graded on a scale of 0 (absent), 1 (mild), 2 (moderate) and 3 (severe). Systemic events include fever, feverishness, fatigue, malaise, myalgia, arthralgia, headache, and nausea. The grading scale for systemic events, including quantitative grading for fever, is included in [Table 11](#). Local events include pruritus, ecchymosis, erythema, induration/swelling, pain, and tenderness. Ecchymosis, erythema, and induration are measured by both functional and measurement grading scales as defined in [Table 10](#).

When calculating the incidence of solicited events, each subject will be counted once at the highest severity following the applicable vaccination, and any repetitions will be ignored. For summaries presented separately for each vaccination, the denominator for percentages will be the number of subjects who received the respective vaccination with non-missing data for the event summarized. For summaries over all vaccinations the denominator will be the number of subjects who received at least one vaccination with non-missing data for the event summarized.

The number and percentage of subjects reporting at least one solicited adverse event of each severity will be summarized for each solicited symptom, any systemic symptom, any local symptom, and any symptoms. For each event the denominator is the number of subjects who received the applicable vaccination with non-missing data for the specific event. The 95% CI calculated using Clopper-Pearson methodology from a binomial distribution (SAS Proc Freq with a binomial option) will be presented ([Table 84](#), [Table 85](#), [Table 86](#)). Logistic regression models will be fit to estimate the effect of prime-boost combination (*PrimeBoost*), Boost dose (*BoostDose*), and interval between vaccinations (*Interval*) on the probability of reporting any local event or reporting any systemic event after either vaccination ([Table 87](#), [Table 88](#)). If statistically significant effects are observed in the model for local events or systemic events, then additional models will be fit for each individual event of that type.

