[Implementation Note: If statistically significant effects defined p-value <0.05 are observed in the model for systemic events then this table should be repeated for additional models which will be fit for each individual systemic event. Any solicited systemic event grade 1 or higher reported within 7 days of study vaccination will count as a reported event.]

Table 89: Number and Percentage of Subjects Experiencing Solicited Events by Symptom, Maximum Severity and Study Group (Safety Population) – Post Any Study Vaccination

| Symptom | Severity | Group 1 2013 3.75+AS03/ 2017 3.75+AS03 (D1-D22) (N=X) | | Group 2 2013 3.75+AS03/ 2017 3.75+AS03 (D1-D121) (N=X) | | Group 3 2013 3.75+AS03/ 2017 15 (D1-D121) (N=X) | | Group 4 2017 3.75+AS03/ 2017 3.75+AS03 (D1-D22) (N=X) | | Group 5 2017 3.75+AS03/ 2017 3.75+AS03 (D1-D121) (N=X) | | Group 6 2017 3.75+AS03/ 2017 15 (D1-D121) (N=X) | | All Subjects (N=X) | |
|----------------------|----------|--|---------------|---|---------------|--|---------------|--|---------------|---|---------------|--|---------------|-----------------------|---------------|
| | | n | % (95% CI) | n | % (95% CI) | n | % (95% CI) | n | % (95% CI) | n | % (95% CI) | n | % (95% CI) | n | % (95% CI) |
| Any Symptom | None | x | xx (xx-xx) | x | xx (xx-xx) | x | xx (xx-xx) | x | xx (xx-xx) | x | xx (xx-xx) | x | xx (xx-xx) | x | xx (xx-xx) |
| | Mild | x | xx (xx-xx) | x | xx (xx-xx) | x | xx (xx-xx) | x | xx (xx-xx) | x | xx (xx-xx) | x | xx (xx-xx) | x | xx (xx-xx) |
| | Moderate | x | xx (xx-xx) | x | xx (xx-xx) | x | xx (xx-xx) | x | xx (xx-xx) | x | xx (xx-xx) | x | xx (xx-xx) | x | xx (xx-xx) |
| | Severe | x | xx (xx-xx) | x | xx (xx-xx) | x | xx (xx-xx) | x | xx (xx-xx) | x | xx (xx-xx) | x | xx (xx-xx) | x | xx (xx-xx) |
| Any Systemic Symptom | None | x | xx (xx-xx) | x | xx (xx-xx) | x | xx (xx-xx) | x | xx (xx-xx) | x | xx (xx-xx) | x | xx (xx-xx) | x | xx (xx-xx) |
| | Mild | x | xx (xx-xx) | x | xx (xx-xx) | x | xx (xx-xx) | x | xx (xx-xx) | x | xx (xx-xx) | x | xx (xx-xx) | x | xx (xx-xx) |
| | Moderate | x | xx (xx-xx) | x | xx (xx-xx) | x | xx (xx-xx) | x | xx (xx-xx) | x | xx (xx-xx) | x | xx (xx-xx) | x | xx (xx-xx) |
| | Severe | x | xx (xx-xx) | x | xx (xx-xx) | x | xx (xx-xx) | x | xx (xx-xx) | x | xx (xx-xx) | x | xx (xx-xx) | x | xx (xx-xx) |
| Fever | None | x | xx (xx-xx) | x | xx (xx-xx) | x | xx (xx-xx) | x | xx (xx-xx) | x | xx (xx-xx) | x | xx (xx-xx) | x | xx (xx-xx) |

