| | Moderate | x | xx (xx-xx) | x | xx (xx-xx) | x | xx (xx-xx) | x | xx (xx-xx) | x | xx (xx-xx) | x | xx (xx-xx) | x | xx (xx-xx) |
| | Severe | x | xx (xx-xx) | x | xx (xx-xx) | x | xx (xx-xx) | x | xx (xx-xx) | x | xx (xx-xx) | x | xx (xx-xx) | x | xx (xx-xx) |

N = Number of subjects in the Safety Population who received any study vaccination; n = Number of subjects reporting event.

95% CI estimated using Clopper-Pearson exact method.

Severity is the maximum severity reported over all solicited symptoms post dosing for each subject.

Tables with similar format:

Table 90: Number and Percentage of Subjects Experiencing Solicited Events by Symptom, Maximum Severity and Study Group (Safety Population) – Post Study Vaccination 1

[Footnote Update] N = Number of subjects in the Safety Population who received the first study vaccination = Number of subjects reporting event.

Table 91: Number and Percentage of Subjects Experiencing Solicited Events by Symptom, Maximum Severity and Study Group (Safety Population) – Post Study Vaccination 2

[Footnote Update] N = Number of subjects in the Safety Population who received the second study vaccination; n = Number of subjects reporting event.

Table 92: Number and Percentage of Subjects Experiencing Solicited Events by Symptom, Severity, Day Post Study Vaccination, and Study Group (Safety Population) – Post Any Study Vaccination

| Symptom | Severity | Pre-Vac | | Post-Vac | | Day 1 | | Day 2 | | Day 3 | | Day 4 | | Day 5 | | Day 6 | | Day 7 | | Day 8+ | |
|---|----------|---------|----|----------|----|-------|----|-------|----|-------|----|-------|----|-------|----|-------|----|-------|----|--------|----|
| | | n | % | n | % | n | % | n | % | n | % | n | % | n | % | n | % | n | % | n | % |
| Group 1: 2013 3.75+AS03/ 2017 3.75+AS03 (D1-D22) (N=X) | | | | | | | | | | | | | | | | | | | | | |
| Any Symptom | None | x | xx | x | xx | x | xx | x | xx | x | xx | x | xx | x | xx | x | xx | x | xx | x | xx |
| | Mild | x | xx | x | xx | x | xx | x | xx | x | xx | x | xx | x | xx | x | xx | x | xx | x | xx |
| | Moderate | x | xx | x | xx | x | xx | x | xx | x | xx | x | xx | x | xx | x | xx | x | xx | x | xx |
| | Severe | x | xx | x | xx | x | xx | x | xx | x | xx | x | xx | x | xx | x | xx | x | xx | x | xx |
| Any Systemic Symptom | None | x | xx | x | xx | x | xx | x | xx | x | xx | x | xx | x | xx | x | xx | x | xx | x | xx |

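### Solicited systemic event counts never use the pre-dose grade; a symptom-by-symptom new-or-worsened count should be added beside them as a supportive analysis

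*SAP*

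**What the plan says.** Protocol 7.1 states that "reactogenicity assessments will be performed immediately prior to each study vaccination to establish baseline". SAP 9.3.1 confirms that the systemic data exist: "Systemic solicited adverse events were collected pre-vaccination".

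The counting rule in SAP 9.3.1 is "each subject will be counted once at the highest severity following the applicable vaccination, and any repetitions will be ignored". The rest of the plan follows it:

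- Table 89 and the tables built on it (90 and 91) carry the footnote "Severity is the maximum severity reported over all solicited symptoms post dosing for each subject".
- The implementation note to Table 88, the logistic model for any systemic event, says "Any solicited systemic event grade 1 or higher reported within 7 days of study vaccination will count as a reported event".
- The model equation in SAP 9.3.1 has terms for prime-boost combination, boost dose, interval and two interactions, and none for pre-dose symptoms.
- Table 95 (McNemar's test) classifies each subject at each dose as having no symptoms or symptoms of at least mild grade.

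The pre-dose grade is displayed only in the Pre-Vac column of Tables 92–94. Laboratory parameters, by contrast, are summarized as change from baseline (SAP 9.6).

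The protocol itself sets the conventional rule. Section 11.6.2 takes the most severe response over follow-up and splits it into none against any grade.

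**The concern.** Solicited reactogenicity is a primary safety outcome. With an endpoint of none against Grade 1 or higher, one unchanged Grade 1 symptom makes a subject positive. The plan collects the information that would separate such a symptom from a new one, then leaves it out of every analysis that yields a rate, an odds ratio or a p-value.

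The Pre-Vac column does not close the gap. It gives marginal counts by symptom and grade, so a reader sees how many subjects had a headache before the dose but not whether the same subjects make up the post-dose count. Listing 11 does not help either, because its alternate-etiology field covers Grade 3 events only, while background symptoms are mostly mild.

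Two things are at stake: how much of the reported incidence belongs to the vaccine, and whether arm and dose contrasts are distorted.

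**Working it through.** **The plan's own figures.** Protocol Table 12 (SAP Table 6) gives a 95% chance of seeing at least one event in an arm of 30 at a 10% event rate. The formula 1 − (1 − 0.10)^30 gives 95.8%, so the figure is reproduced to within a point. Neither this table nor the minimum detectable differences depend on the counting rule, so no stated figure changes.

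**Direction for rates.** Any subject with a new or worsened symptom has a post-dose grade of at least 1 and is also positive under the SAP rule. The SAP's positives therefore contain all the new-or-worsened positives, and the SAP rate cannot be lower. This step needs no assumption.

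**Size with equal prevalence.** Let t be the new-or-worsened rate and q the share with a pre-dose symptom that persists after the dose without worsening, independent of the reaction. Then

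observed rate = t + (1 − t)q,

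and with the same q in both arms the observed difference is (1 − q) times the true one. Both t and q are assumed here, since the documents give neither.

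| q | t = 50% observed as | 60% v 40% observed as | difference |
|---|---|---|---|
| 5% | 52.5% | 62% v 43% | 19 points |
| 10% | 55% | 64% v 46% | 18 points |
| 20% | 60% | 68% v 52% | 16 points |

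For a larger contrast, 60% v 30% with 30 per arm (two-sided 5%, pooled z approximation):

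| q | observed | difference | odds ratio | power |
|---|---|---|---|---|
| 0 | 60.0% v 30.0% | 30.0 points | 3.50 | 65% |
| 5% | 62.0% v 33.5% | 28.5 points | 3.24 | 60% |
| 10% | 64.0% v 37.0% | 27.0 points | 3.03 | 55% |
| 20% | 68.0% v 44.0% | 24.0 points | 2.70 | 46% |

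**Unequal prevalence.** Take 60% v 30% again.

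- With q = 15% in the first arm and 5% in the second, the rates become 0.60 + 0.40 × 0.15 = 66.0% and 0.30 + 0.70 × 0.05 = 33.5%. The difference is 32.5 points, wider than the true 30.
- With the two values of q exchanged, the rates are 62.0% and 40.5%, a difference of 21.5 points.
- With 60% in both arms and q of 15% v 5%, the rates are 66% and 62%, a 4-point difference where there is none.

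**Where equal q is plausible.** Randomization supports it at dose 1 and for the boost-dose contrasts that share prime and interval (Groups 2 v 3 and 5 v 6). It is not assured at dose 2 for the 21- versus 120-day contrast, because the pre-dose assessments are then made at different times after the first dose.

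**What can be present before a dose.**

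- Fever: entry requires a temperature below 100.0°F (Protocol 5.1.1) and dose 2 is deferred at 100°F or above (5.2.3). Grade 1 fever starts at 100.4°F, so fever is effectively excluded.
- Before dose 1: residual symptoms of a nearly resolved illness are allowed only if the investigator judges that they will not interfere with safety assessment (5.1.2).
- Before dose 2: "An unresolved or ongoing Grade 1 solicited or unsolicited AE is permissible", but only after a documented determination that it would not make vaccination unsafe or interfere with evaluating responses. The same section postpones dose 2 for symptoms that could confuse the reactogenicity assessment, and withholds it for a Grade 2 event that has not fallen to Grade 1.

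What remains is mainly mild, subjective symptoms.

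**The case against.** The strongest reply is that the SAP does what Protocol 11.6.2 asks. A post-dose maximum split at Grade 1 is the convention, and it never undercounts a safety outcome. That stands, and it is why the conventional counts should stay as the main analysis.

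Four stronger readings are tempting, and the documents do not support them.

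- *The baseline data are discarded.* They are displayed in Tables 92–94. What is missing is the link within a subject.
- *The SAP breaks the protocol's adverse event rule.* Protocol 9.2.1 says "However, if the severity of any pre-existing medical condition increases, it will be recorded as an AE", but that passage concerns conditions present at screening, not solicited symptoms graded before each dose. The principle is similar, but no rule is broken.
- *Dose 1 reactions are counted again at dose 2.* The permission for an ongoing Grade 1 event makes this possible. However, dose 2 comes about 21 or 120 days after dose 1, against a 7-day solicited window, and nothing in the documents suggests that symptoms last that long.
- *Arm contrasts shrink.* They do so only if q is equal across arms and independent of the reaction.

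It is also fair to object that a new-or-worsened definition has its own error. A subject whose Grade 1 headache before the dose resolves, and who then has a genuine Grade 1 reaction on Day 3, becomes a non-event. A comparison of overall maxima would be worse, since a mild headache before the dose would hide new mild fatigue. Both points bear on how the supportive outcome is built, and the first is a reason not to let it replace the conventional one.

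**Conclusion.** The point holds as a limitation of the analysis that is cheap to remedy, not as an error against the protocol. The incidence tables, the Table 88 model and Table 95 make no use of the pre-dose grade. Relative to a new-or-worsened definition this can only raise systemic rates, and the effect falls mainly on mild subjective symptoms and the any-grade endpoint rather than on severe events.

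The size cannot be known from the documents. Under an assumed q of 5–20%, equal across arms and independent of the reaction, a 50% rate is overstated by 2.5–10 points and arm differences are multiplied by 0.95–0.80. Prevalence may well sit at or below the low end, given the screening before each dose. Where q differs between arms, most plausibly in the interval contrast at dose 2, the direction is not predictable. In Table 95 the effect can likewise go either way, because a persisting symptom may turn a discordant pair into a concordant one or the reverse.

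**What to change.** Keep the any-post-dose counts as the main analysis. Add to SAP 9.3.1 a supportive outcome for the seven subjective systemic symptoms (feverishness, fatigue, malaise, myalgia, arthralgia, headache, nausea):

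- For each symptom and dose, the event is a post-dose maximum grade above the grade at that dose's own pre-administration assessment.
- Any systemic event is positive if at least one single symptom is new or worsened. Grades are compared symptom by symptom, never as overall maxima. Fever can enter unchanged, since it is effectively excluded before dosing.
- For summaries over both doses, a subject is positive if positive after either dose.

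Show it beside the conventional results in Tables 84–86, 88, 89–91 and 95, and state that the conventional definition is primary. Note the addition in SAP Section 12, which currently reports no changes from the protocol's analyses, and fix it before unblinding.

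The cost is one derived variable from data already collected, extra table rows and one more model fit. The downside is a second set of counts, and a supportive definition that can miss a true reaction of the same grade as a resolved pre-dose symptom. It should therefore be read next to the conventional counts and not in their place.
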